PI	Principal Investigator
REDCap	Research Electronic Data Capture
SAE	Serious Adverse Event
SUSAR	Suspected Unexpected Serious Adverse Reaction
UIRTSO	Unanticipated Problem Involving Risks to Subjects or Others
WCM	Weill Cornell Medicine
WCINYP	Weill Cornell Imaging NewYork Presbyterian
PCa	Prostate Adenocarcinoma
⁶⁸Ga	Gallium-68
PET	Positron Emission Tomography
ROI	Regions of Interest
PSMA	Prostate Specific Membrane Antigen
Ga-PSMAcyc	Ga-PSMA cyclotron
Ga-PSMAGen	Ga-PSMA generator

1. Protocol Summary

[figure not shown]
Full Title:	Evaluation of a ⁶⁸ Ga Small Molecule PSMA Antagonist Produced by two different Methods
Clinical Phase:	I/II
Principal Investigator:	[name]
Study Description:	Patients with metastatic prostate cancer will undergo two protocol ⁶⁸ Ga-PET scans within 24-48h with ⁶⁸ Ga-PSMA-cyclotron and ⁶⁸ Ga-PSMA-generator radiotracers. The goal of the study is to evaluate repeatability and equivalence across the different ⁶⁸ Ga-PSMA production methods.
Sample Size:	Up to 30 patients will be enrolled in the study as defined by protocol criteria.
Enrollment:	30 patients will be enrolled in this study
Study Population:	Patients with metastatic prostate adenocarcinoma
Enrollment Period:	2 years
Study Design:	Single-dose, non-randomized design. Patients with metastatic prostate adenocarcinoma will be administered a single intravenous dose of each of the study drugs ⁶⁸ Ga-PSMA-cyclotron and ⁶⁸ Ga-PSMA-generator 24-48 hours apart.
Description of Sites/ Facilities Enrolling	
Participants:	This is a single site study. All study procedures will be performed in the NYP/WCMC facilities, CBIC, and WCINYP.
Study Duration:	2 years
Participant Duration:	3 Visits: 1 screening/consent and 2-infusions imaging. The duration of patient participation can be up to 4 weeks, depending on eligibility, and the scheduling and completion of required study visits
Study Agent/Device Name	
Intervention Description:	⁶⁸ Ga-PSMA-cyclotron and ⁶⁸ Ga-PSMA-generator; single dose each, approximately 100-300 mBq.
Primary Objective:	
• To evaluate equivalence of two processes to create ⁶⁸Ga-HBED-PSMA (⁶⁸Ga-PSMA-cyclotron vs. ⁶⁸Ga-PSMA-generator)
Secondary Objectives:	
• Comparative dosimetry and biodistribution (⁶⁸Ga-PSMA-cyclotron vs. ⁶⁸Ga-PSMA-generator), whole body excretion/ metabolism in patients with confirmed metastatic PCa
Exploratory Objectives:	
• Investigate repeatability of whole-body ⁶⁸Ga-PSMA-generator Ki Patlak imaging against that of conventional whole-body ⁶⁸Ga-PSMA- SUV imaging in patients with confirmed metastatic prostate adenocarcinoma.

- Evaluate equivalence of whole-body ⁶⁸Ga-PSMA Ki Patlak imaging between the two processes to create ⁶⁸Ga-HBED-PSMA (⁶⁸GA-PSMA-cyclotron vs. ⁶⁸Ga-PSMA-generator)

Endpoints:

The primary endpoint of this study is to prove equivalence between the cyclotron and generator produced radioisotope. To meet this endpoint we will make a direct comparison of the ⁶⁸GA-PSMA-cyclotron vs. ⁶⁸Ga-PSMA-generator scans obtained within 24-48h. We will measure SUVmean and SUVmax of the same Regions of Interest (ROI) in both scans using the PET analysis software we use in our clinical practice. The two scans will be retrieved and the exact same ROIs will be drawn at the same time for the two scans (software offers a copy-paste function so that no discrepancies exist between the two measurements). The SUVmean and SUVmax obtained from both scans for each Region of Interest will then be analyzed to determine the within-subject coefficient of variation value as measured by the Bland Altman analysis.

1.1 Schema

1.2 Study Objectives

1.2.1 Primary Objectives

- To confirm ^{68}Ga -PSMA-generator repeatability in patients with confirmed metastatic PCa.
- To evaluate equivalence of two processes to create ^{68}Ga -HBED-PSMA (^{68}GA -PSMA-cyclotron vs. ^{68}Ga -PSMA-generator).

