2.5.2 Cyclotron Production

[figure not shown]
Gallium-68 will be produced by **NCM USA LLC**, a NYC-based advanced PET radiopharmaceutical manufacturing and distribution company ([name]) with whom we have an academic-industrial partnership NIH grant to investigate manufacturing this nuclide based on an IND held by the company. In summary, the NCM cyclotron will use enriched (>99% purity) zinc-68 target, the target will first be dissolved in 10-12 N HCl and solution will be passed on AG-50W-X8 resin to separate Zn-68 and elute gallium Gallium-68 as ^{68}Ga - GaCl_3 in 3N HCl. The cyclotron produced ^{68}Ga that will be released by NCM for labeling and formulation of the ^{68}Ga -HBED-PSMA product. The radiochemical purity of the in house product will be required to match and be equivalent to the specifications of the ^{68}Ga -HBED-PSMA generator produced radiopharmaceutical.

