3.1 Overall Design

Thirty patients with metastatic prostate cancer that have undergone standard-of-care staging at WCMC will be considered for enrollment. For this study, enrolled patients will undergo a total of two whole-body dynamic ^{68}Ga -PET scan protocols of at least 0-75 min and at most 0-90 min scan time post injection, depending on the amount of injected dosage. A 6 to 48 hour gap will be introduced between the two scans. The first scan will occur after a baseline clinical evaluation, which will include a history, physical, and baseline lab draw. Blood work will be obtained before, during and after the scan. The radiotracers will be evaluated for repeatability and equivalence across the different production methods. This will include basic pharmacokinetics, distribution, metabolism and excretion.

Up to 30 patients will undergo each two whole-body dynamic scans, initially with ^{68}Ga -PSMAcyc and later with ^{68}Ga -PSMagen (with a minimum time of 6 h and maximum time of 2 days between the two injections). All patients will receive ^{68}Ga -PSMagen from the CBIC core and ^{68}Ga -PSMAcyc from NCM pharmaceuticals at a specific activity of 1-2 Ci/ μmol , the typical specific activity used in published clinical trials with ^{68}Ga -PSMA (10).

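### Section 1.2.1 makes generator repeatability a primary objective, but no patient is scanned twice with the generator product, so the planned analyses measure generator–cyclotron agreement instead

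*Combined protocol and SAP*

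**What the plan says.** **Objectives.** Section 1.2.1 has two primary objectives. The first is to confirm "PSMA-generator repeatability in patients with confirmed metastatic PCa"; the second is equivalence of the two production processes. The Protocol Summary has only one: "To evaluate equivalence of two processes to create" the tracer. The first exploratory bullet, in the Protocol Summary and in Section 1.2.3, begins "Investigate repeatability of whole-body" and concerns generator Ki imaging compared with SUV imaging.

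**Endpoint and purpose.** The Protocol Summary states: "The primary endpoint of this study is to prove equivalence between the cyclotron and generator produced radioisotope". Sections 7.10 and 10 also give equivalence as the study's specific purpose.

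**Design.** Under Study Design in the Protocol Summary, patients "will be administered a single intravenous dose of each of the study drugs". Section 3.1 says "Up to 30 patients will undergo each two whole-body dynamic scans, initially with" the cyclotron product and later with the generator product. The footnote to the Section 6.1 schedule and Section 12 likewise give one scan per product, and Section 7.1 says the repeat imaging uses the second tracer. No section plans a second generator scan, even in a subset.

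**Analysis.** SUVmean and SUVmax from the two scans are "analyzed to determine the within-subject coefficient of variation value as measured by the Bland Altman analysis". Section 12 also plans a mixed-model repeatability r with a single grouping factor, a Pearson correlation described as showing repeatability, and intraclass correlations (ICCs) for two groups that it does not define. It ends by presenting the Bland-Altman analysis as proof of repeatability. Section 7.1 takes repeatability from the generator and cyclotron scans together.

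**The concern.** Repeatability of a product is the variation between repeated measurements with that product in the same patient. It needs at least two injections of that product in some patients. Here the only within-patient contrast is generator against cyclotron, so the difference contains generator error, cyclotron error and any tendency of individual patients to take up the two products differently.

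If the plan is followed as written, the trial will report one of its two Section 1.2.1 primary objectives as met by a statistic that measures something else. The generator product is the comparator here, so a repeatability figure attached to it could later be reused as a benchmark.

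**Working it through.** **1. The plan's own figure.** The plan gives no target or precision for repeatability. Its one calculated figure, 18.47% power with 22 patients, is for an odds-ratio equality test. The odds ratio, proportions, sidedness and group convention are not given, so it can be neither reproduced nor refuted, and it has no bearing on repeatability.

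**2. Count of same-product pairs.** Scans per patient: 2 (Sections 3.1 and 7.1). Scans per product per patient: 1 (Protocol Summary; Sections 3.1, 6.1, 7.1 and 12). Same-product pairs: 0, for 22 or 30 patients. The dynamic passes within a scan share one injection and are not replicates.

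**3. What the pair estimates.** On the log-SUV scale, for one region per patient, write generator = P + I_g + e_g and cyclotron = P + I_c + e_c. Let the patient variance be b, the interaction variance i per product, and the error variances g (generator) and c (cyclotron), with independent errors. Then

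- Var(difference) = 2i + g + c
- planned within-subject SD = √[(2i + g + c)/2]
- ratio to the true generator error SD = √[(2i/g + 1 + c/g)/2]

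The ratio is guaranteed to be 1 only when i = 0 and c = g. The documents give none of these variances, so the ratios below are assumptions:

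| i/g | c/g = 0.5 | c/g = 1 | c/g = 2 |
|---|---|---|---|
| 0 | 0.87 | 1.00 | 1.22 |
| 0.25 | 1.00 | 1.12 | 1.32 |
| 1 | 1.32 | 1.41 | 1.58 |

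The 1.00 at i/g = 0.25, c/g = 0.5 arises because the two departures happen to cancel. In the limit i = 0, c = 0 the ratio is √0.5 = 0.71, an understatement of 29%. The planned statistic can therefore err in either direction.

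**4. More patients do not help.** Assume b = 0.16, g = c and i + g = 0.0225. Every case below has variance 0.1825 per product, covariance 0.16 and within-subject SD √(0.045/2) = 0.150:

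| i/g | g | generator error SD |
|---|---|---|
| 0 | 0.0225 | 15.0% |
| 0.25 | 0.0180 | 13.4% |
| 1 | 0.01125 | 10.6% |

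The observable variances and covariance are identical, so the data cannot tell these cases apart. Sampling precision is a separate matter: with one region per patient, the relative SE of the within-subject variance is √[2/(n−1)] = 0.31 for n = 22 and 0.26 for n = 30.

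**5. The ICCs.** If the two undefined groups are the products and regions serve as replicates, the per-product ICC is (b + s²)/(b + s² + v), where s is the scan error SD shared by all regions and v the region variance. With b = 0.16, raising s from 0.05 to 0.20 raises the ICC from 0.80 to 0.83 (assumed v = 0.04) or from 0.39 to 0.44 (assumed v = 0.25). More scan error looks like better repeatability. If the groups are something else, such as the reference and suspicious regions in Section 12, there is still no same-product pair behind them.

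**The case against.** **The trial's stated decision is equivalence.** The synopsis objective, the primary endpoint and the purpose in Sections 7.10 and 10 concern equivalence alone. No sample size or success rule is tied to generator repeatability, and the 30% rule in Section 12 concludes only on equivalence. This stands and sets the severity. A reader might infer that the primary comparison fails; the documents do not support that, because the cross-product pair is the right data for it.

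**The protocol uses repeatability loosely.** The Protocol Summary and Section 3.1 speak of repeatability and equivalence across production methods, and Section 7.1 says openly which scans are used. That is fair for those passages. It does not rescue Section 1.2.1, which names the generator product and lists equivalence separately.

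**The products may behave alike.** Section 2.5.2 says the "radiochemical purity of the in house product will be required to match and be equivalent to the specifications of the" generator product, which may make interaction small. Section 12, however, accepts cyclotron specific activity of 0.1–2.0 Ci/µmol against 1–2 for generator, citing small-animal work designed around a 20-fold range but giving no result there. A reader might infer from the wider range that interaction exists. It does not show that: variable specific activity points first to a mean shift or extra cyclotron error. The conditions are unverified, not shown to be false.

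**The data at least bound generator error.** A reader might infer that the planned CV is a conservative bound. It is not, as the 0.87 shows. Only the SD of the paired differences, not divided by √2, is at least the generator error SD. That holds in the population and with independent errors. At c/g = 0.5 and i = 0, the sample value falls below the generator SD in 13% of trials with n = 22 and 9% with n = 30. Regions are copied between scans and the same scanner is preferred, so shared error is plausible. With equal errors, no interaction and error correlation ρ, the ratio is √[2(1−ρ)], below 1 once ρ exceeds 0.5 (0.77 at an assumed ρ of 0.7).

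**Conclusion.** The point holds and should be fixed. That there are 0 same-product pairs follows from the documents alone and needs no assumption. It means that generator repeatability, for SUV in Section 1.2.1 and for Ki in the exploratory objectives, is not estimated by this design. The planned analyses give between-product agreement. Reading them as generator repeatability requires no patient-by-product interaction and equal error variances, neither of which is stated; with one scan per product, the data cannot test for interaction.

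The size figures (0.87 to 1.58, and 10.6% to 15.0% generator error behind the same data) illustrate assumed variances and are not predictions for this trial. The equivalence endpoint and the 30% rule are untouched by this point.

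**What to change.** By amendment, with no added scans, patients or measurements:

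1. Remove generator repeatability from Section 1.2.1, so that equivalence is the only primary objective, as in the Protocol Summary, the primary endpoint and Sections 7.10 and 10.
2. Reword the first exploratory bullet, in the Protocol Summary and Section 1.2.3, to compare between-product agreement of Ki imaging with that of SUV imaging.
3. In Section 12, relabel the mixed-model r, the Pearson sentence and the closing Bland-Altman sentence as between-product agreement. Delete the ICC comparison of two groups, or define the groups and label the ICC as agreement.
4. Make the same wording change in Section 7.1 and in the study-goal sentences of the Protocol Summary and Section 3.1.
5. Report the between-product within-subject CV and limits of agreement with confidence intervals, and do not present them as generator repeatability. For scale, an assumed within-subject SD of 0.150, with one region per patient, has a 95% interval of about 0.12 to 0.21 with 22 patients and 0.12 to 0.20 with 30.

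If a statement on generator error is still wanted, use only the upper confidence limit of the SD of paired differences (not divided by √2). State the independent-errors assumption and note that error shared between the two scans could break it.

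**Cost.** The amendment needs IRB approval before it is implemented (Section 11.2.1), and the sponsor gives up a repeatability claim. Keeping that claim would require generator–generator pairs in at least a subset, with a precision target of their own. That would be a change of design, which this point does not require.

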1.2.2 Secondary Objectives

- Comparative dosimetry and biodistribution (^{68}GA -PSMA-cyclotron vs. ^{68}Ga -PSMA-generator), whole body excretion/metabolism in patients with confirmed metastatic PCa.

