6.1 Schedule of Assessments

Table 1. Schedule of trial events

	Screening- Visit 1 (Baseline or D0)	Imaging 1* (Visit 2 or D1)	Imaging 2* (Visit 3 or D2)
ICF	X		
Medical History	X		
Physical Exam	X		X
Review medications	X		
CBC	X		
Serum BUN and Creatinine	X		
AST, ALT, ALP, bil, albumin	X		
Review of prior imaging	X		
Adverse event monitoring		X	X
⁶⁸Ga-PSMA administration		X	X
⁶⁸Ga-PSMA PET scans		X	X
Research Blood draws **		X	X

*Two scans with ⁶⁸Ga-PSMA-cyclotron and ⁶⁸Ga-PSMA-generator radiotracers will be performed at least 24h apart (max 48h)
 
** Research blood draws will be performed only in a subset of patients (3-5) and are not required for participation in the study. The planned timepoints are as follows: pre tracer injection, 5 minutes (+/- 10 minutes) 15 minutes (+/- 10 minutes), 30 minutes (+/-10 minutes), 60 minutes (+/-10 minutes). A blood draw will also be performed after each scan (12 blood draws in total per patient at most) (for details refer to section 6.1.2.2).
			

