6.1.2.2 Serum Blood Draws

A subset of patients will have serum blood draws (approximately 5 ml) for pharmacokinetic analysis. This is **only** required in a subset (3-5 patients) as a smaller number of patients will be needed to generalize organ and lesional dosimetry. The planned timepoints are as follows: pre tracer injection, 5 minutes (+/- 10 minutes) 15 minutes (+/- 10 minutes), 30 minutes (+/-10 minutes), 60 minutes (+/-10 minutes). A blood draw will also be performed after each scan (12 blood draws in total per patient at most). This will be done through the IV placed to administer the PET tracer during the imaging visit. Apart from routine laboratory tests, samples will also be evaluated for the presence of ⁶⁸Ga, as well as ⁶⁶Ga, potential contaminants for generator-produced and cyclotron-produced products. Blood counts, liver function tests, and creatinine levels will also be monitored before, during, and after imaging evaluation/radiotracer injection. Apart from routine laboratory tests, samples will also be evaluated for the presence of ⁶⁸Ga, as well as ⁶⁶Ga, potential contaminants for generator-produced and cyclotron-produced radiotracers, respectively. Images will also be evaluated for location of radiotracer uptake, as well as excretion and organ-specific dosimetry.

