Moreover, the number of bed positions will be adjusted to cover a field of view from top of the skull to mid-thigh of an average human adult for each pass. All PET scans will be conducted with patients in a supine position with the arms comfortably positioned and secured by the side of the patient. All whole-body PET passes of each subject will be uni-directional, i.e. they will be performed along the same axial direction (cranio-caudal or caudo-cranial).

The PET data from at least the last six whole-body scan passes will be summed up and reconstructed at each bed position such that the product of total acquisition time per bed position from all passes and injected activity is at least 7.5 MBq/kg*min or a total scan time of 90min is reached. The resulting composite static PET images will then be combined with the same method as that employed for conventional static PET images at each bed position and the composite Standardized Uptake Value (SUV) static PET images will be calculated. In the meantime, the dynamic ⁶⁸Ga-PSMA concentration in the blood plasma (input function) will also be derived from the dynamic PET images at the pelvis, as estimated from the 0-10min p.i. of the initial dynamic pelvic PET scan and the corresponding pelvic beds of the subsequent set of whole-body PET passes. For that purpose, regions of interest will be drawn in the lumen of the abdominal section of the descending aorta that is included in the pelvic bed position. The blood pool image regions will be drawn as far as possible from the neighboring aortic wall to minimize any partial volume effects. The image derived input function data will then be fitted to the measured blood samples data for validation and enhanced accuracy. Subsequently, the images from all the dynamic PET whole-body passes and the image-derived input function will be fitted to the Patlak graphical model on a voxel-by-voxel basis to produce whole-body ⁶⁸Ga-PSMA net uptake rate constant (Ki) images. During the PET scan procedure, the patient will be allowed to get off from the couch in between the dynamic whole-body passes, if required (such as for a bathroom break).

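### The secondary objective promises metabolism, which nothing in the plan measures, and whole-body excretion, which can only be imaged to 75-90 min with unrecorded voids

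*Combined protocol and SAP*

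**What the plan says.** Section 1.2.2 and the Protocol Summary in Section 1 make the between-product comparison cover "whole body excretion/metabolism in patients with confirmed metastatic PCa". Section 3.1 says of the evaluation: "This will include basic pharmacokinetics, distribution, metabolism and excretion".

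These are the measurements offered in support:

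- **Blood.** The footnote to the Section 6.1 schedule states: "Research blood draws will be performed only in a subset of patients (3-5) and are not required for participation in the study". Section 6.1.2.2 gives the count: "A blood draw will also be performed after each scan (12 blood draws in total per patient at most"). On the assay it says "Apart from routine laboratory tests, samples will also be evaluated for the presence of" 68Ga and 66Ga.
- **Images.** Section 6.1.2.2 adds: "Images will also be evaluated for location of radiotracer uptake, as well as excretion and organ-specific dosimetry". Under Section 7.1 the pelvis is imaged dynamically for the first 10 min. Whole-body passes then run to at least 75 and at most 90 min, with bed positions "adjusted to cover a field of view from top of the skull to mid-thigh of an average human adult for each pass".
- **Urine.** Neither the schedule nor Section 6.1.2.2 lists a urine collection. Section 7.1 has patients hydrated and encouraged to void before imaging. During the scan they are "allowed to get off from the couch in between the dynamic whole-body passes, if required (such as for a bathroom break"). Nothing asks for the time or content of a void to be recorded.
- **Analysis.** Section 12 covers repeatability and agreement of SUVmax and SUVmean. It defines no endpoint or comparison for excretion or metabolism.

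**The concern.** An objective should name something that the data can show. Metabolism means knowing how much of the measured activity is still intact tracer. PET and counting for 68Ga or 66Ga detect the nuclide, whatever molecule carries it. Total excretion means accounting for activity that has left the body, and here that activity can leave the field of view unmeasured.

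Two things are at stake. The report could claim a comparison of metabolism for which there are no data. And the bladder comparison, which carries most of the information on urinary excretion, can be distorted by behaviour unrelated to the product: a patient who takes a bathroom break in one session and not in the other shows lower bladder activity in the first. Section 7.11 says that the order is not randomized, so the design does not balance such differences between products.

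**Working it through.** **1. Specimens.** Six time points per scan (pre-injection, 5, 15, 30 and 60 min, and post-scan) × 2 scans = 12 draws, which reproduces the plan's maximum. All 12 are blood. They come from 3-5 of up to 30 patients and are optional.

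**2. Metabolism.** Of the two sources of data, blood gives routine laboratory values and nuclide presence, and images give total nuclide concentration. Neither distinguishes parent compound from metabolite. The number of patients with metabolite data is 0.

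**3. Excretion.** Two direct routes to a total would be counting excreta, or taking injected minus retained activity over the whole body. The first is not planned. The second is not proposed, and coverage ending at mid-thigh would not support it. What remains is organ activity on the images: kidneys, liver, gut and bladder all lie inside the field of view.

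**4. Voids.** Injection coincides with the start of the dynamic PET, so the void encouraged before imaging removes none of that session's tracer. The void that matters is the one permitted between passes. If it removes a fraction *f* of bladder activity, two identical products would show a bladder ratio of 1 − *f* just after the break (void session over no-void session). The documents give no value for *f*, so I put no size on it. Table 1 shows why it matters for dose: bladder wall has 0.481 rad/mCi, second only to kidneys at 0.969. At 3.3 mCi this is 0.481 × 3.3 = 1.59 rad, as tabulated.

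**5. Share of the dosimetry integral after the last pass.** The documents give no half-life. I assume *T* = 67.7 min, with a range of 67-68.3.

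With physical decay only and immediate uptake, the share after time *t* is 2^(−*t*/*T*):

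- *t* = 75: 2^(−75/67.7) = 0.464 (range 0.460-0.467)
- *t* = 90: 2^(−90/67.7) = 0.398 (range 0.394-0.401)

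For an organ with washout, let λp = ln2/67.7 and λb = ln2/(biological half-life), with that half-life assumed to be 2-6 h. The share is exp[−(λp+λb)*t*]:

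- *t* = 75: 0.30-0.40
- *t* = 90: 0.24-0.33

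For a bladder filling at those same assumed rates and never emptied, activity is proportional to exp(−λp*t*)·[1 − exp(−λb*t*)]. The share is {exp(−λp*t*)/λp − exp[−(λp+λb)*t*]/(λp+λb)} ÷ {1/λp − 1/(λp+λb)}:

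- *t* = 75: 0.75-0.80
- *t* = 90: 0.68-0.73

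So the unobserved share depends on the organ, and under these assumptions it is largest for the bladder.

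**The case against.** The best defence is that the plan does state a route for excretion. Section 6.1.2.2 takes it from the images, and Section 7.1 supplies repeated passes over the excretory organs in both sessions. Renal, hepatobiliary and bladder time-activity can be compared within patient. A void between passes would appear as a fall in bladder activity, and breaks are allowed only if needed. The primary equivalence rule uses SUVmean and SUVmax and does not depend on excretion or metabolism.

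All of that stands, and it limits the point. A reader might infer that the whole objective cannot be answered; the documents do not support that, because image-derived excretion to 75-90 min is available. A reader might also think that leaving out the lower legs defeats the excretion comparison. It only blocks excretion by difference, which the plan does not propose. Nor does 40-46% apply to every organ, as step 5 shows, and a late tail affects the completeness of dosimetry without making excretion unobservable.

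The defence does not reach metabolism, for which no measurement is described. Nor does it cover the missing void record: without void times, a fall between passes has to be interpreted with no confirmation that a void took place.

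**Conclusion.** The point holds in a limited form. Metabolism is promised and not measured. Total whole-body excretion cannot be directly quantified, because there is no urine measurement and imaging ends at 75-90 min. Image-derived excretion can be compared between products, but an unrecorded void in one session can be misread as a product difference in bladder activity and bladder-wall dose.

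The extrapolated share of 40-46% assumes physical decay only, immediate uptake and a half-life of about 67.7 min. The washout and bladder figures also rest on assumed biological half-lives of 2-6 h. The conclusion on metabolism needs none of these assumptions. The primary endpoint is unaffected.

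**What to change.** - Delete metabolism from the objective in Sections 1 and 1.2.2 and from the design statement in Section 3.1.
- In the same places, restate excretion as image-derived renal, hepatobiliary and bladder time-activity up to the last pass (75-90 min), compared within patient between products. Add the regions, times and paired comparison to Section 12.
- Record the time of every void in both sessions, and account for it in the bladder comparison, for example by using the fall in bladder activity between adjacent passes.
- State that the dosimetry integral after the last pass is extrapolated, and use the same method for both products.

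The cost is a narrower claim, some rewording and a short void log. Counting voided urine would be needed only if the sponsor wants to keep a claim about total urinary excretion. It would be an added procedure, and this point does not depend on it.
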